PTT	Partial Thromboplastin Time
SAE	Serious Adverse Event
SADR	Serious Adverse Drug Reaction
SAS	Safety Analysis Set
SDS	Standard Deviation score
SMR	Service Medical Rendu
TSH	Thyroid-Stimulating Hormone
ULIS	Units localized for school inclusion

2 Responsible parties

In this document physician refers to the individual overall responsible for the conduct of the Non-Interventional Study (NIS) at a study site.

3 Abstract

- **Title:** French registry of children treated with Norditropin[®] for short stature due to Noonan Syndrome-NS (PASS)

Planned milestones:

Milestone	Planned date
Start of data collection (FPFV)	March 2022
Last Patient First Visit (LPFV)	March 2024
Last Patient Last Visit (LPLV)	March 2028
Study progress reports	Monthly update during implementation, inclusion & follow-up
Interim report of study results	October 2025
Final report	August 2028

Background and Rationale:

Norditropin[®] (NN-220; somatropin; Novo Nordisk A/S, Denmark), a recombinant human growth therapy (rhGH) produced by genetic recombinant technology, is currently the sole approved medication for the treatment of short stature due to NS in France. In October 2020, the Transparency Committee (CT- *Commission de Transparence*) rated the actual clinical benefit (SMR- *Service Medical Rendu*) of Norditropin[®] as “important” and issued a favourable opinion for inclusion of Norditropin[®] on the list of reimbursed proprietary medicinal products in NS children with short stature (< -2 SDS)(1).

Despite the existing literature documenting the effect of GH therapy on height outcomes, long-term effectiveness and safety data associated with Norditropin[®] treatment is needed. Furthermore, information on quality of life in NS patients remains scarce. Hence, the CT has requested the development of a national registry of NS children with short stature and treated with Norditropin[®] until adulthood. Data should be available within five years. This registry shall provide information on long-term clinical evolution of these patients (e.g adult height and quality of life) and on the safety profile of Norditropin[®] (notably the risk of tumour, effect on glucose metabolism and cardiac defects). The CT has also recommended that data collection be defined in collaboration with French reference and competence centres.

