8.1.1.2 Secondary endpoints

Secondary objective-1: To evaluate the long-term safety profile of Norditropin®.

All drug related adverse reactions (ADR), serious adverse drug reactions (SADR), serious adverse events (SAE) and adverse events (AE) will be recorded and described up to the end of growth development or end of follow-up if earlier. The endpoints related to the secondary objective-1 are listed in [Table 3](#).

Table 3 Secondary endpoints in relation to secondary objective 1

Title of endpoint	Time frame	Unit
Number of adverse drug reactions (ADR)	From start of Norditropin® until end of follow-up	Count of events
Number of serious adverse drug reactions (SADR),	From start of Norditropin® until end of follow-up	Count of events
Number of serious adverse events (SAE)	From start of Norditropin® until end of follow-up	Count of events
Number of adverse events (AE)	From start of Norditropin® until end of follow-up	Count of events

Secondary objective-2: To describe the socio-demographic and clinical characteristics of patients. The endpoints related to the secondary objective-2 are listed in [Table 4](#).

Table 4 Secondary endpoints in relation to secondary objective 2

Title of endpoint	Time frame	Unit
Socio-demographic		
Education	From start of Norditropin® treatment until end of follow-up	NA
School level	From start of Norditropin® treatment until end of follow-up	NA
Educational measures	From start of Norditropin® treatment until end of follow-up	NA
Clinical characteristics		

Title of endpoint	Time frame	Unit
Tanner stage	At all visits	NA
Change in pulse rate	From start of Norditropin® treatment until end of follow-up	Beats per minute
Change in diastolic blood pressure	From start of Norditropin® treatment until end of follow-up	mm Hg
Change in systolic blood pressure	From start of Norditropin® treatment until end of follow-up	mm Hg
Change in corrected QT-interval (Electrocardiogram)	From start of Norditropin® treatment until end of follow-up	msec
Change in echocardiogram parameters	From start of Norditropin® treatment until end of follow-up	mm (Left ventricular interventricular septal maximum thickness in diastole) mm (Left ventricular end diastolic diameter) % (Left Ventricular Fractional Shortening (LVFS)) % (Left Ventricular Ejection Fraction (LVEF)) Cm/s (Diastolic function (Ea)) Cm/s (Diastolic function (Aa))

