Number of modifications (change in dosage/ temporary stop)	From start of Norditropin® treatment until end of follow-up	Count of events
Reasons for treatment modifications	From start of Norditropin® treatment until end of follow-up	NA
Duration of temporary stop	From start of Norditropin® treatment until end of follow-up	Months

Title of endpoint	Time frame	Unit
Total duration of Norditropin [®] treatment	From start of Norditropin [®] treatment until end of follow-up	Years
Total cumulative dose of Norditropin [®] treatment	From start of Norditropin [®] treatment until end of follow-up	mg/kg
Other NS treatments		
Type and number of concomitant treatments	At all visits	Count of events
Type and number of concomitant treatments linked to an adverse event	At all visits	Count of events

Secondary objective-4: To describe the NS in terms of auxological characteristics, diagnosis and NS comorbidities.

The endpoints related to the secondary objective-4 are listed in [Table 6](#).

Table 6 Secondary endpoints in relation to secondary objective 4

Title of endpoint	Time frame	Unit
Auxological characteristics		
Change in weight	From start of Norditropin [®] treatment until end of follow-up	SDS
Change in body mass index (BMI)	From start of Norditropin [®] treatment until end of follow-up	Kg/m ²
Change in bone age	From start of Norditropin [®] treatment until end of follow-up	year
Change in height velocity	From start of Norditropin [®] treatment until end of follow-up	cm/year and SDS/year
Type and number of NS comorbidities	At all visits	NA

Secondary objective-5: To evaluate the evolution of Health-Related Quality of Life (HRQoL) of patients/Legally Acceptable Representative (LAR).

The endpoints related to the secondary objective-5 are listed in [Table 7](#).

Table 7 Secondary endpoint in relation to secondary objective 5

Title of endpoint	Time frame	Unit
Change in HRQoL score (PedsQL)	From start of Norditropin [®] treatment until end of follow-up	NA

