8.2.10 Other assessments

Socio-demographic characteristics

- Sex (baseline)
- Age at start of Norditropin[®] treatment in years (baseline)

Clinical characteristics

- Age at puberty onset (at baseline or one of the follow-up visit)
- Age at onset of menstruations (female only) (at baseline or one of the follow-up visit)
- IGFBP-3 level (baseline)
- TSH level (baseline)
- FT4 level (baseline)
- Haemostasis parameters

Norditropin[®] treatment patterns

- Date at start (baseline)
- Dose of Norditropin[®] at treatment start in mg/k/day (baseline)
- Date at the end of treatment (at one of the follow-up visit)
- Dose of Norditropin[®] in mg/k/day at the end of follow-up (at one of the follow-up visit)

GH treatment history

- Type and number of previous GH treatments (baseline)
- Duration of GH treatment before Norditropin[®] in years (baseline)
- Dose of GH treatment before Norditropin[®] in mg/kg/day (baseline)
- Type of GH treatment following Norditropin[®] (at one of the follow-up visit)
- Date of start of GH treatment following Norditropin[®] (at one of the follow-up visit)
- Dose of GH treatment following Norditropin[®] in mg/kg/day (at one of the follow-up visit)

Auxological characteristics

- Age at gestational age in weeks (baseline)
- Weight at birth, 1 year, 2 years and 3 years of age in kg (baseline)

- Length at birth, 1 year, 2 years and 3 years of age in cm (baseline)
- Head circumference at birth, 1 year, 2 years and 3 years of age in cm (baseline)
- Height velocity in the first year/six months preceding Norditropin® treatment start
- Mother's height in cm (baseline)
- Father's height in cm (baseline)
- AH in SDS (at one of the follow-up visit)

Diagnosis

- Familial form of Noonan (baseline)
- Parent affected (baseline)
- Age of clinical diagnosis of NS (baseline)
- Molecular diagnosis performed (at one of the follow-up visit)
- Date of molecular diagnosis (at one of the follow-up visit)
- Molecular diagnosis (type of NS-related genes mutated, and variant identified) (at one of the follow-up visit)

NS comorbidities

- Type and number of NS comorbidities (baseline)

Health-Related Quality of Life (PROs): PedsQL

HRQoL will be assessed on incident patients only. They will be asked and their parents to complete the PedsQL questionnaire annually.

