AMH	Continuous variable	Endpoints
LH	Continuous variable	Endpoints
FSH	Continuous variable	Endpoints
Oestradiol	Continuous variable	Endpoints
Testosterone	Continuous variable	Endpoints
Auxology		
Gestational age at birth	Continuous variable	Endpoints
Head circumference at birth , at 1 year, 2 years and 3 years of age	Continuous variable	Endpoints
Birth weight, at 1 year, 2 years and 3 years of age	Continuous variable	Endpoints
Birth length at 1 year, 2 years and 3 years	Continuous variable	Endpoints
Weight at start of Norditropin®	Continuous variable	Endpoints

Variables	Operational Definition	Measurement
Height at start of Norditropin®	Continuous variable	Endpoints
Parents 'height	Continuous variable	Endpoints
BMI	Continuous variable	Endpoints
Height velocity in the first year/6 months preceding Norditropin® treatment start	Continuous variable	Endpoints
Height velocity	Continuous variable	Endpoints
Adult height (AH)	Continuous variable	Endpoints
Bone age	Continuous variable	Endpoints
Diagnosis		
Familial form of Noonan	Categorical variable 
 • Yes • No 	Endpoints
Parent affected (if yes to familial form of Noonan)	Categorical variant 
 • Mother • Father 	
Age at clinical diagnosis of NS	Continuous variable	Endpoints
Molecular diagnosis performed	Categorical variable 
 • Yes • No 	
Date of molecular diagnosis of NS (if yes to molecular diagnosis performed)	Continuous variable	Endpoints
Molecular diagnosis (type of NS-related genes mutated and variant identified)	Categorical variable 
 • PTPN1 • KRAS • RAF1 • RIT1 • SHOC2 • SOS1 • SOS2 • Other 	Endpoints
NS comorbidities		
NS comorbidities	Categorical variable 
 • Cardiac defects including pulmonary valve stenosis and hypertrophic cardiomyopathy • Orthopaedic issues (pectus, scoliosis) • Anorchia in males 	Endpoints
Therapeutic care		
Dose of Norditropin® treatment	Continuous variable Recorded at each study visit	Endpoints

Variables	Operational Definition	Measurement
Total duration of Norditropin® treatment	Continuous variable From start of Norditropin® treatment until end of follow-up	Endpoints
Total cumulative of Norditropin® dose	Continuous variable Total dose of Norditropin® administered from start of treatment until end of treatment	Endpoints

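### As defined in Table 10, the Noonan comorbidity endpoint merges distinct diagnoses into three groups with no open category, so it cannot separate or fully count them

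*Protocol*

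**What the plan says.** Four places in the protocol bear on this endpoint.

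- **Section 8.1.1.2, Table 6** (secondary objective 4) lists "Type and number of NS comorbidities" with a time frame of all visits. The flow chart in Table 9 agrees and marks NS comorbidities at baseline and at each six-monthly visit to M48.
- **Section 8.3, Table 10**, in its operational definition column, makes the variable categorical with three levels. The first is "Cardiac defects including pulmonary valve stenosis and hypertrophic cardiomyopathy". The second is orthopaedic issues, with pectus and scoliosis in brackets. The third is "Anorchia in males". No further level follows.
- **Section 8.2.10** lists the same type-and-number item but tags it as a baseline assessment.
- **Sections 3 and 6.2** say that the authority that requested the registry wants it to inform the safety profile, notably "the risk of tumour, effect on glucose metabolism and cardiac defects".

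**The concern.** Type and number are the two things this endpoint is meant to report, and both depend on how finely the comorbidities are coded. With one level for every cardiac defect, the type reported is only that the child has some cardiac defect. The two cardiac diagnoses that the protocol itself names are not distinguished. The number becomes the number of groups a child falls into, not the number of conditions the child has.

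Two things are at stake. Secondary objective 4 is to describe NS in these children, comorbidities included, and a reader of the final report will expect the frequency of each main diagnosis at treatment start. Cardiac defects are also one of the three topics that the authority singled out, so this is the group where merging costs most.

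The missing open category adds to this. Table 9, under other NS treatments, focuses on medication for attention deficit hyperactivity disorder and on thyroid hormones. A condition treated with these has no level in the comorbidity list, so the treatment could be recorded as NS-related while the condition has no code.

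**Working it through.** No sample size, power or error rate enters here. The check is to apply the Table 10 levels to example records and compare the result with coding by diagnosis. The records are illustrations and not data from the protocol. It is assumed that several levels can be ticked for one child; if only one can be chosen, the count can never exceed 1.

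| Record | Count on Table 10 levels | Count by diagnosis |
|---|---|---|
| Pulmonary valve stenosis at baseline | 1 | 1 |
| Same child, hypertrophic cardiomyopathy added later | 1 | 2 |
| Stenosis, cardiomyopathy, pectus and scoliosis | 2 | 4 |
| One NS comorbidity outside the three groups | 0 | 1 |

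On the Table 10 levels the maximum count is 3 in boys (three levels) and 2 in girls (the anorchia level cannot apply). In the second row neither type nor number changes when the new diagnosis appears.

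**Can other variables supply what is lost?**

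- *Adverse events.* All are recorded regardless of causality (Section 8.2.9) and coded to MedDRA Preferred Term (Section 8.7.4), and cardiac events are named as events of special interest (Section 10.5). A new cardiomyopathy during prospective follow-up can be identified this way. A defect already present at treatment start is not an on-treatment event, so this route does not supply it.
- *Echocardiography.* Table 4 lists six parameters, among them "Left ventricular interventricular septal maximum thickness in diastole", and Table 9 schedules them at baseline and yearly. Septal thickness may point to cardiomyopathy. None of the six measures the pulmonary valve, so stenosis cannot be identified from them.
- *Comorbidities not related to NS.* Table 10 gives no levels for this variable and Table 9 marks it at baseline only. By its title it does not cover NS comorbidities.

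**How many patients have retrospective years?** The inputs in Section 8.5 are 50 incident patients, up to 30 prevalent starters per year from 2010, 79% of sites taking part and 80% of eligible patients included. Taking ten years to 2020 gives 10 × 30 = 300 prevalent patients.

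- Total: (50 + 300) × 0.79 × 0.80 = 221.2, which reproduces the protocol's 221.
- Prevalent: 300 × 0.79 × 0.80 = 189.6, about 190.
- Share: 300 / 350 = 86%.

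These are the protocol's own upper limits. For such patients' years before inclusion, Section 10.1 limits adverse event collection to the time after consent, although Table 3 gives a time frame from the start of Norditropin, so coverage is doubtful. Section 8.4 does not require data that routine care has not produced, so echocardiograms may be absent too. The comorbidity item is then a main source for diagnoses in most of the expected cohort.

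**Timing.** Tables 6 and 9 say every visit; Section 8.2.10 says baseline. Under the baseline-only reading the change over time in the second row is not collected here at all. The merging of diagnoses and the missing open category remain under either reading.

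**The case against.** The strongest reply is that a row in Table 10 need not be the data-entry code. The same table puts six echocardiogram parameters in one row and five blood count components in another, and each has its own unit in Table 4. The comorbidity levels name stenosis, cardiomyopathy, pectus and scoliosis individually, and the case report form, a stand-alone document listed in Annex 1, may record them separately. Nothing in the protocol says that number means number of groups. This stands as a limit: the point concerns the endpoint as defined in Table 10, and the form cannot be checked. It does not repair the definition, because for this variable the groups are given as the levels of a categorical variable.

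Three further replies carry some weight.

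- The word 'including' keeps the cardiac level open, so an unnamed cardiac defect is still counted as cardiac. This is right; what is lost is the distinction within the level.
- The missing open category is not unique. Molecular diagnosis, injection frequency, reasons for modification and concomitant medication have one; education, school level, educational measures and type of modification do not. The comparison therefore supports the point without proving it. The lack of a 'none' level is no defect, since no box ticked can mean 0.
- Section 6.2 says a scientific committee of reference-centre physicians supported the choice of data, and grouping can be a legitimate choice for description. That would justify reporting groups as well as diagnoses, but not a count that ignores diagnoses.

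A reader might infer that the registry would miss a new cardiac defect in any child who already has one. The documents do not support that: adverse event coding, the cardiac event of special interest and yearly septal thickness all remain. The authority's cardiac question also belongs to the safety profile, which is secondary objective 1, and not only to this item.

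**Conclusion.** The point holds as a defect of definition in one descriptive secondary endpoint. On the Table 10 levels, the endpoint cannot separate the named cardiac or orthopaedic diagnoses, cannot show a second diagnosis within a group, and cannot count an NS comorbidity outside the three groups.

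The loss lies mainly in diagnoses present at treatment start and in the pre-inclusion years of prevalent patients, who make up about 190 of the 221 expected at most. It does not extend to the study's ability to detect new cardiac events in prospective follow-up, and no numerical figure in the protocol is affected. The effect on the mean count or on reported frequencies cannot be estimated, because the protocol gives no comorbidity frequencies.

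The conclusion assumes that the endpoint is tabulated on the levels as printed. If the case report form already records diagnoses separately, only the text and the counting rule need to change. The correction should be made, but it is a modest one.

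**What to change.** - In Table 10, and in the eCRF if it does not already do so, replace the three levels with separate yes/no items: pulmonary valve stenosis; hypertrophic cardiomyopathy; other cardiac defect; pectus; scoliosis; anorchia (males); other NS comorbidity (specify).
- Define number as the count of yes items, with 0 allowed, and report each item separately. The present groups can be kept as a derived summary.
- Reconcile the baseline tag in Section 8.2.10 with the all-visit schedule in Tables 6 and 9.

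The cost is a few more tick boxes and slightly more entry per visit. The information comes from medical records that are already a data source, and no new assessment is imposed on patients.

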Frequency of injections per week	Categorical variable 
 • 6 days/7 • 7 days/7 • Other 	Endpoints
Type of treatment modifications	Categorical variable 
 • Increase in dosage • Decrease in dosage • Temporary stop • Permanent stop 	Endpoints
Duration of temporary stop	Continuous variable	Endpoints
Number of treatment modifications	Categorical variable 
 • From 1 to 5 	Endpoints
Reasons for treatment modifications	Categorical variable 
 • Safety (occurrence of ARs or AEs) • Growth too fast • Growth too slow • Patient's or parents/LAR choice • Other 	Endpoints
Type of previous GH treatments	Categorical variable	Endpoints
Dose of previous GH treatment at start	Continuous variable	Endpoints
Total duration of previous GH treatment	Continuous variable From start of previous GH treatment until the end of treatment	Endpoints
Type of GH treatment following Norditropin®	Categorical variable	Endpoints
Dose of GH treatment following Norditropin®	Continuous variable	Endpoints
Date of GH treatment following Norditropin®	Continuous variable	Endpoints
Concomitant medications	Categorical variable 
 • ADHD medications including methylphenidate • Cardiac medications • Thyroid hormones • Sex steroids including testosterone and oestrogen 	Endpoints

Variables	Operational Definition	Measurement
	
 Other 	
HRQoL		
PedsQL score	Categorical variable 
 From 0 to100 	Endpoints
Safety		
Incidence rate	Number of new cases per population at risk over the follow-up period (per person-time)	Endpoints
Other co-variates (controls)		
Sites 'geographic location	Categorical variable : 
 Ile-De France North-West West East South-East South-West 	Bias
Sites 'activity size s	Continuous variable Defined by the number of children treated with Norditropin® for short stature due to NS managed over a year	Bias

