8.7 Data analysis

8.7.1 Definition of analysis sets

The site populations will be defined as follows:

- Contacted sites: all reference and competence centres in France will be solicited to participate in this study
- Participating sites: all sites that agreed to participate in the study
- Active sites: all sites that included at least one eligible patient

The sites main characteristics (localisation, size) will be compared to ensure that the active sites are representative at the national level.

There are 3 patients population considered in this study:

- Overall population: all patients included in the eCRF,
- Full Analysis Set (FAS): all patients included in the eCRF and meeting all selection criteria. All secondary analyses will be performed on FAS.

- Growth Analysis Set (GAS): all patients from the FAS for which the primary criteria can be evaluated, i.e. height measurements available until the end of the 5-year follow-up or until NAH is reached, whatever occurs first.

The subgroups of interest for analyses are defined as follows:

- Norditropin[®] treatment duration: depending on age of onset and age at puberty onset, the patients may have shorter or longer time under GH treatment, which may highly influence auxological outcomes
- Mutated gene: PTPN11, SOC2, other

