8.7.2.1 Analysis of primary endpoint

The main growth evolution endpoint is defined as the change in height Standard Deviation Score (SDS) between baseline and the end of follow-up or GH, whatever occurs first. It will be described overall and depending on the duration of Norditropin[®] treatment.

Height SDS is defined as the deviation of patient's height from the standard French growth curve (normal values). It is obtained from the patient's height by subtracting the normal mean and dividing by the normal standard deviation.

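### Table 10 ends total Norditropin treatment duration at end of follow-up rather than end of treatment, so children who stop or switch while still followed are credited with treatment they did not have

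*Protocol*

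**What the plan says.** In Protocol section 8.3, the operational-definition column of Table 10 gives total duration of Norditropin treatment as "From start of Norditropin® treatment until end of follow-up". The next row, cumulative dose, reads "Total dose of Norditropin® administered from start of treatment until end of treatment". Further down, total duration of previous GH treatment reads "From start of previous GH treatment until the end of treatment".

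Section 8.7.1 names treatment duration as a subgroup of interest because "the patients may have shorter or longer time under GH treatment, which may highly influence auxological outcomes". Section 8.7.2.1 says of the primary endpoint: "It will be described overall and depending on the duration of Norditropin[®] treatment". Total duration of treatment, in years, is also a secondary endpoint in Table 5 (section 8.1.1.2).

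The protocol expects treatment to end before follow-up in some children. Table 10 codes "Permanent stop" as a type of treatment modification. Section 8.2.10 collects the date treatment ended and any growth hormone given after Norditropin. Section 8.7.4 analyses post-treatment adverse events. Section 8.2.7 does not list stopping Norditropin among the withdrawal reasons.

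**The concern.** A variable meant to measure exposure has been given the closing date of observation. The two dates coincide for a child still on Norditropin when follow-up ends. They separate for a child who stops permanently or changes to another growth hormone and remains in the registry.

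If the analysis follows Table 10, such a child has the same treatment duration as one treated throughout, and height gain by duration mixes short and long exposure. Incident children start treatment at inclusion, so all those followed to M48 would have a duration of about 4 years whatever their actual exposure. Among them the variable could not do what section 8.7.1 wants of it. The secondary endpoint would be overstated for the same children.

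**Working it through.** No sample size, power or precision figure in the protocol depends on this definition, so there is no stated figure to reproduce for it. The check is a comparison of definitions, then an illustration.

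**Definitions side by side (Table 10)**

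| Variable | Starts | Ends |
|---|---|---|
| Total duration of Norditropin | start of Norditropin | end of follow-up |
| Cumulative Norditropin dose | start of Norditropin | end of treatment |
| Duration of previous GH treatment | start of that treatment | end of that treatment |

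The table itself distinguishes the two end points. For cumulative dose the choice makes no numerical difference, because no dose accrues after stopping. For duration it does.

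**Effect on one child.** Assume 4 years from treatment start to end of follow-up.

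Overstatement factor = (start to end of follow-up) / (start to end of treatment).

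| Permanent stop at | Table 10 | Actual | Factor |
|---|---|---|---|
| year 4 | 4 | 4 | 4/4 = 1.00 |
| year 3 | 4 | 3 | 4/3 = 1.33 |
| year 2 | 4 | 2 | 4/2 = 2.00 |
| year 1 | 4 | 1 | 4/1 = 4.00 |

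**Effect on mean duration.** The share of stoppers s is an assumption, since the protocol gives none. Let stops be spread evenly over the 4 years, so that stoppers average 2 years.

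Mean actual duration = 4(1 − s) + 2s. Overstatement = 4 / mean − 1.

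| s | Mean actual (years) | Overstatement |
|---|---|---|
| 0% | 4.0 | 0% |
| 5% | 3.9 | 2.6% |
| 10% | 3.8 | 5.3% |
| 20% | 3.6 | 11.1% |
| 30% | 3.4 | 17.6% |

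**Temporary stops.** These are recorded with their length. With 6 months of interruption and treatment otherwise continued to year 4, gross duration is 4 years and net duration 3.5 (4/3.5 = 1.14). Table 10 does not say whether gross or net is meant.

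**Table 11.** Its precision is 1.96 × 0.20 / √177 = 2.95%, as stated. Treatment duration does not enter the formula.

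**The case against.** The strongest defence is that the wording is a stock observation window. The same phrase is the time frame of nearly every endpoint in Tables 2 to 7, and Table 5 applies it to cumulative dose and to length of temporary stops, where it can only be a window. That holds for Table 5, which needs no edit. It does not carry over to Table 10, where the column is the operational definition and comparable rows name the end of treatment.

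A second defence is that section 8.7.1 describes the subgroup as time under treatment, that neither it nor section 8.7.2.1 names the Table 10 variable as the classifier, and that derivations can be left to the SAP. It is true that misplacing stoppers follows only if Table 10 is applied literally. But the protocol has fixed a definition. A SAP that follows it carries the error forward, and one that departs from it contradicts the protocol.

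Several stronger readings are tempting but unsupported:
- **That duration is the only planned breakdown of the primary endpoint.** Mutated gene is also a subgroup (8.7.1), and section 8.7.2 applies the subgroups to the primary endpoint. Duration is only the one named again in 8.7.2.1.
- **That the variable measures study follow-up alone.** Its clock starts at treatment start, so for prevalent children it includes treatment before inclusion.
- **That all patients would get about 4 years.** This concerns incident children. On the section 8.5 assumptions they number about 50 × 30/38 × 0.80 ≈ 32 of 221 (14%). Prevalent children who stopped can still be misclassified.
- **That the bias in height gain can be set against the 2.95% precision.** That figure concerns the overall mean at 177 patients, and any shift in a subgroup mean needs an assumed share of stoppers and an assumed growth pattern.
- **That average dose per year would be wrong.** No such endpoint is planned, and dose is recorded directly in mg/kg/day.
- **That temporary stops must be subtracted.** This is a choice, and their length is reported separately.

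**Conclusion.** The point stands as a definition error in one row of Table 10. As written, the rule overstates treatment duration for children who stop permanently or switch while still followed, by a factor of 1.33 to 4 for stops between year 3 and year 1 of a 4-year span. It conflicts with the stated purpose of the duration subgroup used to describe the primary endpoint, and it misstates a secondary endpoint.

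The size across the registry is unknown: zero if every child is treated without interruption to the end of follow-up, and otherwise dependent on a share of stoppers that the protocol does not give. The analyses at risk are descriptive. The overall primary mean and Table 11 do not change. No data are lost, because the end-of-treatment date and the length of temporary stops are collected. It should be corrected before analysis.

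**What to change.** In Table 10, define total duration of Norditropin treatment as the time from treatment start to the earlier of end of Norditropin treatment and end of follow-up. State whether recorded temporary stops are subtracted. Say in sections 8.7.1 and 8.7.2.1 that this variable forms the duration subgroup and the breakdown of the primary endpoint. Table 5 can stay as it is, since its column is a time frame.

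The cost is one table row and a cross-reference in two sections, with no new data collection and no change to visits, sample size or patient care.
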